#### **7.4.7.1 First Report of Diarrhoea**

- Obtain history of onset and duration of diarrhoea
- Description of number of stools and stool composition (e.g. watery, blood, mucus in stool)
- Assess patient for fever, abdominal pain, cramps, distension, bloating, nausea, vomiting, dizziness, weakness (i.e., rule out risk for sepsis, bowel obstruction, dehydration)
- Medication profile (i.e., to identify any diarrhoeagenic agents)
- Dietary profile (i.e., to identify diarrhoea-enhancing foods)

Proactively look for occurrence of diarrhoea after start of CB-103 treatment. Call patients at home, if necessary, to detect diarrhoea early during the first 8 weeks. If no problems occur, instruct the patient to call when a problem does arise.

#### **7.4.7.2 Management of Diarrhoea**

##### **General measures:**

- Stop all lactose-containing products, alcohol
- Stop laxatives, bulk fibre (e.g., Metamucil®, Procter & Gamble), and stool softeners (docusate sodium; Colace, Roberts)
- Drink 8 to 10 large glasses of clear liquids per day (e.g., water, Pedialyte® (Ross), Gatorade (Quaker), broth)
- Eat frequent small meals (e.g., bananas, rice, apple sauce, Ensure®, toast)
- Stop high-osmolar food supplements such as Ensure Plus and Jevity Plus (with fibre)

It is recommended that patients be provided loperamide tablets. It is mandatory that patients are instructed on the use of loperamide at cycle 1 in order to manage signs or symptoms of diarrhoea at home. Patients should be instructed to start oral loperamide (initial administration of 4 mg, then 2 mg every 4 hours (maximum of 16 mg/day) at the first sign of loose stool or symptoms of abdominal pain. These instructions should be provided at each cycle and the investigational site should ensure that the patient understood the instruction. At the beginning of each cycle, each patient should be specifically questioned regarding any experience of diarrhoea or diarrhoea related symptoms. If symptoms were experienced, then the investigational site should question the patient regarding the actions taken for these symptoms.

### **7.4.7.3 Treatment of Diarrhoea Grade 1 or 2**

Diarrhoea grade 1 or 2 will be treated with standard loperamide (initially at first administration 4 mg, then 2 mg every 4 hours [maximum of 16 mg/day] or after each unformed stool).

#### **12-24 hours later:**

##### **Diarrhoea resolved**

- Continue instructions for dietary modification
- Gradually add solid foods to diet
- Discontinue loperamide after 12-hours diarrhoea-free interval

##### **Diarrhoea unresolved**

Persisting diarrhoea grade 1 or 2 will be treated with addition of opium tincture, dihydrocodeine tartrate tablets/injections and start early on with corticosteroids which is the recommended treatment for the development of goblet cell metaplasia seen with other NOTCH inhibitors. Treatment should be accompanied by monitoring the patient's condition (to rule out dehydration, sepsis, ileus), medical check and selected workup if patient does not need hospitalisation (see Section 7.4.7.5 for diarrhoea work-up). Observe patient for response to antidiarrheal treatment and may also consider treatment with high dose corticosteroids.

Persisting diarrhoea grade 3 or 4 may be treated with hospitalisation, high dose loperamide (initially 4 mg, then 2 mg every 2 hours), addition of opium tincture or dihydrocodeine tartrate tablets/injections and with high dose corticosteroids to potentially inhibit the development of the goblet cell metaplasia seen with other NOTCH inhibitors. Furthermore, start of i.v. fluids, parenteral nutrition and antibiotics as needed with monitoring of patients' condition (to rule out dehydration, sepsis, ileus), medical check and workup (perform appropriate additional testing) should be started immediately. Observe patient for response.

#### **After 12-24 hours:**

##### **Diarrhoea resolved**

- Continue instructions for dietary modification
- Gradually add solid foods to diet
- Discontinue loperamide and/or other treatment after 12-hours diarrhoea-free interval

## Diarrhoea unresolved

- If diarrhoea still persisting (NCI CTC grades 1 and 2), after 2 x 24 hours with high dose loperamide, opiates and corticosteroids then admit to hospital and employ measures as for grade 3 and 4 until diarrhoea resolved.
- If diarrhoea still persisting and progressed to NCI grades 3 and 4, employ measures described below.

### 7.4.7.4 Treatment of Diarrhoea Grade 3 or 4

Severe diarrhoea grade 3 or 4 may be treated with hospitalisation, high dose loperamide (initially 4 mg, then 2 mg every 2 hours, addition of opium tincture or dihydrocodeine tartrate tablets/injections as well as early start of administration of corticosteroids as being the recommended treatment for goblet cell metaplasia observed in patients treated with other NOTCH inhibitors. Furthermore, start of i.v. fluids, parenteral nutrition and antibiotics as needed with monitoring of patients' condition (to rule out dehydration, sepsis, ileus), medical check and workup (see Section 7.4.7.5 for diarrhoea work-up). Observe patient for response.

#### After 12-24 hours:

- If diarrhoea persisting administer high dose corticosteroids and consider subcutaneous (s.c.) Sandostatin/octreotide (100-500 µg three times daily [TID])
- Continue i.v. fluids, parenteral nutrition and antibiotics as needed
- If diarrhoea grade 3 or 4 still persists patients should receive besides corticosteroids opium tincture or dihydrocodeine tartrate injections s.c. or intramuscular (i.m.)
- If diarrhoea grade 3 or 4 is still persisting s.c. Sandostatin/octreotide (500-1000 µg TID) should be administered.
- To control and/or resolve diarrhoea, next cycle of treatment should be delayed by 1 or 2 weeks. Treatment should be continued only when diarrhoea resolved.

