### 7.4.6.1.6 Gastro-Intestinal Toxicities (Diarrhoea, Nausea)

In non-clinical studies in different species (dog, rat, mouse), CB-103 administered at different doses and administration schedules did not show any gastro-intestinal toxicities, e.g. diarrhoea, weight loss. However, as other NOTCH inhibitors (GSIs, mABs) have shown diarrhoea as their major DLT, there might be a risk for CB-103 to also develop gastro-intestinal toxicities. In the event that diarrhoea is observed in clinical trial patients, the following algorithm for CB-103 dose modifications should be followed. Furthermore, Sections 7.4.7.2 to 7.4.7.4 provide a management plan for the occurrence of diarrhoea with a description of measures and treatment suggestions.

**Table 9** Dose modifications for gastro-intestinal toxicities

Dose Modifications for CB-103	
Worst Toxicity CTCAE Grade unless otherwise specified (Value)	At any time during a cycle of CB-103 (including intended day of dosing)
Gastro-intestinal toxicities	
Grade 1	Maintain dose level
Grade 2 (see Sections 7.4.7.2 to 7.4.7.4 for treatment algorithm)	Omit dose administration until recovery to Grade ≤ 1 or baseline then continue at current dose level if grade 2 toxicity persisted for ≤ than 7 days. If grade 2 toxicity persisted for more than 7 days decrease dose by 1 dose level after resolution to Grade 0 or baseline
Grade 3 (see Section 7.4.7.2 to 7.4.7.4 for treatment algorithm)	Omit dose administration until recovery to Grade ≤ 1 or baseline then decrease the next scheduled dose by 1 dose level
Grade 4 (see Section 7.4.7.2 to 7.4.7.4 for treatment algorithm)	Omit dose administration until recovery to Grade ≤ 1 or baseline then decrease the next scheduled dose by 1 dose level In the event Grade 4 toxicity lasts > 24 hours despite maximal medical attention discontinue treatment. If grade 4 toxicity lasts < 24 hours reduce dose by 1 dose level at next cycle If toxicity recurs discontinue treatment.
All grades	At the first sign of abdominal cramping, loose stools, or onset of diarrhoea, the patient should be treated according to Sections 7.4.7.2 to 7.4.7.4 according to the recommended treatment algorithm. Omit dose administration of CB-103 for ≥ CTCAE grade 2 diarrhoea only if diarrhoea could not be controlled despite the use of optimal anti-diarrhoea treatments.

 Common Terminology Criteria for Adverse Events (CTCAE Version 4.03)

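### The hold and restart rules for CB-103 after diarrhoea disagree between Table 9 and Section 7.4.7.4, and within Table 9 itself

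*Protocol*

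**What the plan says.** Section 7.4.6.1.6 introduces Table 9 by stating that if diarrhoea occurs, "the following algorithm for CB-103 dose modifications should be followed". It describes Sections 7.4.7.2 to 7.4.7.4 as a management plan with measures and suggested treatments.

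Table 9:

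- **Grade 3 row, and the opening of the grade 4 row:** "Omit dose administration until recovery to Grade ≤ 1 or baseline then decrease the next scheduled dose by 1 dose level".
- **Grade 4 row, continued:** "In the event Grade 4 toxicity lasts > 24 hours despite maximal medical attention discontinue treatment", and then "If grade 4 toxicity lasts < 24 hours reduce dose by 1 dose level at next cycle".
- **Grade 2 row:** the hold is unconditional. If grade 2 lasts more than 7 days, the reduced dose starts only at grade 0 or baseline.
- **'All grades' row:** "Omit dose administration of CB-103 for ≥ CTCAE grade 2 diarrhoea only if diarrhoea could not be controlled" by optimal anti-diarrhoeal treatment.

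Section 7.4.7.4, on grade 3 or 4 diarrhoea, ends with its own dosing instruction: to control or resolve the diarrhoea, the "next cycle of treatment should be delayed by 1 or 2 weeks. Treatment should be continued only when diarrhoea resolved".

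SAP Section 2.1.4 adds no restart rule. It refers back to protocol Section 7.4.5, which itself points to 7.4.6.1.

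**The concern.** A site treating grade 3 diarrhoea finds two restart instructions. Under one, the patient resumes at a reduced dose as soon as the event has fallen to grade 1. Under the other, the patient waits for resolution and for a cycle delayed by a week or two. For diarrhoea that loperamide has brought under control, one row of Table 9 stops the drug and another does not. Read literally, the second allows dosing to continue through controlled grade 3 or 4 diarrhoea.

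Section 7.4.6.1 applies these rules during and after cycle 1 in Part A and throughout Part B. What is at stake is patient safety and uniform conduct across sites. Related diarrhoea had already been reported in 20% of 41 patients (Section 2.5.6; all grades), and Section 7.4.6.1.6 names diarrhoea as the major DLT of other NOTCH inhibitors.

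**Working it through.** The plan gives no figure to reproduce. The check is a comparison of text, followed by one piece of arithmetic on the 14-day limit.

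**1. Restart after grade 3 (and grade 4 under 24 hours)**

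| Element | Table 9 | Last bullet of 7.4.7.4 |
|---|---|---|
| Recovery threshold | Grade ≤ 1 or baseline | 'Resolved', no grade given |
| Timing | Next scheduled dose; dosing is daily (Section 7.4), so there is no minimum wait | Next cycle delayed by 1 or 2 weeks |
| Dose | One level lower | Not mentioned |

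The timing rules differ on their face. The threshold differs if 'resolved' means more than grade 1, and Section 7.4.7.3 points that way. Under its 'unresolved' heading it places "If diarrhoea still persisting (NCI CTC grades 1 and 2"), and under its 'resolved' heading it says "Discontinue loperamide and/or other treatment after 12-hours diarrhoea-free interval". That is inference from a neighbouring section, because 7.4.7.4 does not define the word. Its silence on dose is a gap and not a contradiction, so Table 9's one-level reduction still applies.

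**2. Condition for holding, inside Table 9**

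Take grade 3 diarrhoea controlled by optimal treatment. The grade 3 row omits CB-103. The 'All grades' row omits it for grade 2 or higher only when control fails, so here it does not. Both rows apply to the same patient.

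**3. Time of the grade 4 reduction, inside Table 9**

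The row opens with the next scheduled dose after recovery. For grade 4 under 24 hours it then says the next cycle. If recovery comes mid-cycle these are different days, and the row does not say what the patient takes in between.

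**4. Grade 4 over 24 hours**

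Table 9 discontinues. Section 7.4.7.4 says treatment continues *only* when diarrhoea has resolved. That is a necessary condition for continuing and does not grant permission to restart. The two statements are compatible.

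**5. The 14-day limit**

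Sections 7.4.5 and 9.2.4 take a patient off study after a continuous interruption of more than 14 days. Let D be the cycle day of the first omitted dose and w the delay in days. The next cycle is due on day 29.

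*Reading A: the drug is held until the delayed next cycle.* Days missed = (29 − D) + w.

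- w = 7: 36 − D exceeds 14 when D ≤ 21 (D = 21 gives 15, D = 22 gives 14). That is 21 of 28 start days.
- w = 14: 43 − D exceeds 14 when D ≤ 28 (D = 28 gives 15). That is 28 of 28 start days.

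*Reading B: dosing resumes within the current cycle and only the next cycle is delayed.* The gap is 36 − 29 = 7 or 43 − 29 = 14 days. Neither exceeds 14, so 0 of 28.

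The result therefore depends wholly on the reading. Patients withdrawn for a DLT under Section 9.2.4, including those with cycle 1 diarrhoea of grade 3 or higher for at least 72 hours despite optimal treatment, fall outside this comparison.

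**The case against.** The best defence is that the protocol already assigns roles. Table 9 is called the dose-modification algorithm, Section 7.4.6.1 tells investigators to follow it, and 7.4.7.2 to 7.4.7.4 are described as suggestions. The delay bullet also closes a sequence for diarrhoea that persists through escalating treatment, so an event that falls quickly to grade 1 would simply follow Table 9. This narrows the conflict but does not remove it. The bullet is worded as a dosing instruction, Table 9's own rows send sites to these sections for treatment, and precedence is never stated.

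A second defence is that the 'All grades' sentence is the diarrhoea-specific qualifier of general gastrointestinal rows. That is plausible for grade 2. For grades 3 and 4 it would defeat the unconditional hold, and the protocol does not say that it is meant to.

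Third, Section 7.4.5 leaves reductions and resumption to the investigator and requires Sponsor approval of any dose adjustment in Part A cycle 1. Interim data were also mild: 73.3% of adverse events were grade 1, 21% grade 2 and 5.7% grade 3, which together make 100%. Diarrhoea is not among the listed serious events. All of this stands, and it limits the severity.

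Three stronger inferences are tempting and not supported:

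- **That 7.4.7.4 lets patients restart after grade 4 lasting over 24 hours.** It does not, for the reason in step 4.
- **That following 7.4.7.4 forces patients off study under the 14-day rule.** This holds only on Reading A.
- **That the choice of rule changes the dose-determining set.** A hold from day 21 or earlier to the end of cycle 1 leaves at most 20 dosing days against the 21 required (Section 10.1). That again needs Reading A, and cycle 1 adjustments pass through the Sponsor. It is a possibility that the documents do not establish.

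**Conclusion.** The point holds in three places: restart timing, and probably threshold, between Table 9 and 7.4.7.4 for grade 3 and for grade 4 under 24 hours; the condition for holding within Table 9; and the timing of the reduction within the grade 4 row. The restart timing and the two Table 9 items rest on the text as written. The threshold part also assumes that 'resolved' carries the sense it has in 7.4.7.3.

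This is a minor to moderate clarification of a safety rule. It has no effect on sample size or error rates, and the 14-day arithmetic is not evidence of harm in itself. It deserves correction because sites should not have to choose between conflicting dosing instructions.

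**What to change.** - **Section 7.4.7.4:** replace the last bullet with a sentence such as: *CB-103 is held, restarted, reduced or discontinued according to Table 9 and Section 7.4.5.*
- **Table 9, hold condition:** limit 'only if not controlled' to grade 2 diarrhoea, repeat it in the grade 2 row, and leave the grade 3 and 4 hold unconditional.
- **Table 9, grade 4 row:** keep one time for the reduction after an event under 24 hours, namely the next scheduled dose after recovery. Leave the discontinuation for more than 24 hours as it is.
- **Threshold:** the clinical team confirms one recovery threshold. At the same time it should settle the grade 2 rule for more than 7 days, which asks for grade 0 or baseline and so is stricter than the grade 3 and 4 rows.

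The cost is protocol wording only. The threshold and the limit to grade 2 are clinical decisions, since the first could loosen the 7.4.7.4 rule and the second narrows a condition that now covers grade 2 and above.

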### 7.4.7.5 Diarrhoea Workup

Perform appropriate tests (American Gastroenterological Association [AGA] Technical Review on the Evaluation and Management of Chronic Diarrhoea; Fine and Schiller, 1999).

#### Spot stool analysis

- Collect stool separating it from urine (special containers, analysis immediately, exceptionally freeze samples)
- Blood
- Faecal leukocytes (Wright's staining and microscopy) or
- *C. difficile* toxin

- Faecal cultures such as *Shigella* and pathogenic *E. coli* - enterotoxigenic, enterohaemorrhagic etc., possibly *Aeromonas*, *Pleisiomonas* (if suspected exposure to contaminated water)

### Endoscopic examinations

Endoscopic examinations may be considered only if absolutely necessary. The bowel is likely to be fragile with evidence of colitis and thus great care and caution must be exercised in undertaking these invasive procedures.

- Gastroscopy to obtain jejunal fluid - re. bacterial overgrowth for cultures and biopsy of proximal jejunum to assess extent of inflammatory jejunitis
- Sigmoidoscopy - reassessment of colitis

### 7.4.8 Sample Size in Part A and Part B

The sample size of Part A of the study depends on the number of patients to be enrolled in each dose level during the dose escalation with at least 3 and up to 6 patients enrolled per dose cohort. Depending on the BLRM, additional patients may be enrolled in some dose cohorts.

The sample size of Part B will depend on the number of patients being enrolled in each expansion arm. For each expansion arm it is planned to have at least 10 patients enrolled and to continue enrolment in each arm to at least 20 patients based on an interim futility analysis. The table below shows the current calculation of sample size for Part A and Part B of the study.

**Table 12** Sample size in Part A and Part B of this study

Escalation Part A	Dose Levels 1-11	MTD/RP2D confirmatory cohort	Expansion Part B	Total Study
N (patients)	55 pts*	45 pts*	100-140 pts	200-240 pts**

\* Depending on the BLRM, additional patients may be enrolled in some dose cohorts. Based on the decision of the CRC approximately 45 patients in total may be enrolled in the MTD/RP2D confirmatory cohort to confirm safety before opening Part B.

\*\* Includes the eligible patients from the MTD/RP2D confirmatory cohort

## **7.5 CONCOMITANT THERAPY**

### **7.5.1 Permitted Concomitant Therapy**

Concomitant therapy includes any medication, e.g., prescription drugs, over-the-counter drugs (OTCs), approved dietary and herbal supplements, nutritional supplements and any non-medication interventions (e.g., individual psychotherapy, smoking cessation therapy, physical therapy and rehabilitative therapy) used by a patient within 14 days of the planned 1st dose administration of CB-103. All concomitant medications taken within 14 days prior to planned first dose administration, as well as all new and ongoing concomitant therapy(ies) must be reported to the Investigator and recorded on the eCRF along with:

- Reason for use
- Dates of administration including start and end dates
- Dosage information including dose and frequency

Any diagnostic procedure and all medication administered to manage adverse events during the study will be according to standard of care and at the discretion of the Investigator and must be recorded on the Adverse Event eCRF with the exception of prohibited medications included in Section 7.5.2 below.

Patients who use oral or injectable contraceptives, hormone-replacement therapy, or other maintenance therapy should continue their use, which should be recorded. Dosing should always be used in the dose-range according to the approved local prescribing information.

Stable doses of medications administered for chronic diseases (e.g. hypertension) are allowed. The use of low molecular weight heparin (as an anticoagulant) is permitted.

### **7.5.2 Prohibited Concomitant Therapy**

Refer to the "[LIST OF PROHIBITED MEDICATIONS](#)" in the synopsis.

## 8. VISIT SCHEDULE AND STUDY ASSESSMENTS

### 8.1 DESCRIPTION OF STUDY ASSESSMENTS

All examinations listed below will be performed according to the Schedule of Assessments outlined in [Appendix 1](#) and [Appendix 2](#).

#### Phase I, Part A – Escalation:

- All patients from each dose cohort in Part A will stay overnight at the hospital for 1 night following their first CB-103 administration (C1D1) to allow for 24-hour PK sampling and ECG monitoring. During this time the patients will be closely monitored for safety. The overnight stays may not be required if reduced ECG and PK sampling is implemented.

In case CB-103 is given BID, one more overnight hospital stays at Day 8 in cycle 1 may be necessary to allow late samples collection.

- Patients will then undergo daily visits for 2 days following the overnight monitoring on Day 1 at the hospital, and will get their CB-103 doses administered in the hospital. Patients will stay at the hospital for at least 3 hours following each administration to allow safety reporting.
- Weekly visits to monitor safety and perform ECG monitoring and PK sampling are planned during the rest of the treatment period for the 1st cycle of CB-103 (28 days).
- Every 2 weeks visits to monitor safety and perform PK sampling are planned from cycle 2 until the completion of cycle 6.
- EOT visit within 14 days after the last dose of CB-103 (within the 6 cycles period).
- Safety follow-up visit (End-of-Study) for each patient within 28 days after the last dose of CB-103.
- Survival follow-up (e.g. per telephone) for 1 year is planned every three months after the End-of-study visit or after the last treatment cycle (if outside of the 6 cycles period).
- Further visits might be considered, depending on the health status of the patient, as determined by the treating Investigator of the respective investigational site.
- More frequent laboratory safety tests (e.g., to closely monitor the liver function), are possible and can be performed outside the study site for those patients leaving far away, if necessary. The laboratory reference ranges from the local laboratories must be collected, and filed in the laboratory report together with the patients' medical records. Care should be taken that any outliers possibly produced by the local laboratory findings are investigated at the study site.

Note: for those patients who may have the option to continue treatment after cycle 6, the subsequent visits are planned every 4 weeks if no medical issue or complication occurred in the previous cycles.

**Phase I, Part A - MTD/RP2D confirmatory cohort and Phase IIA, Part B – Expansion:**

**For patients with solid tumours who are not hospitalized:**

- Patients will undergo daily visits for 3 days and will get their CB-103 doses administered in the hospital. Patients will stay for at least 3 hours following each administration of CB-103 to allow safety reporting with the exception of the first day where the patients should stay for up to 8 hours post-dose.

In case CB-103 is given BID, one more overnight hospital stays at Day 8 in cycle 1 may be necessary to allow late samples collection.

- Weekly visits to monitor safety and perform ECG monitoring and PK sampling are planned during the rest of the treatment period for the 1st cycle of CB-103 (28 days).
- Every 2 weeks visits to monitor safety and perform PK sampling are planned from cycle 2 until the completion of cycle 6.
- After cycle 6, subsequent visits are planned every 4 weeks if no medical issue or complication occurred in the previous cycles.
- End-of-Treatment (EOT) visit within 14 days after the last dose of CB-103 (within the 12 cycles period).
- Safety follow-up visit (End-of-Study) for each patient within 28 days after the last dose of CB-103.
- Survival follow-up (e.g. per telephone) for 1 year is planned every three months after the End-of-Study or after the last treatment cycle (if outside of the 12 cycles period), and every six months thereafter for the 2nd year.
- Further visits might be considered, depending on the health status of the patient, as determined by the treating Investigator of the respective investigational site.
- More frequent laboratory safety tests (e.g., to closely monitor the liver function), are possible and can be performed outside the study site for those patients living far away, if necessary. The laboratory reference ranges from the local laboratories must be collected and filed in the laboratory report together with the patients' medical records. Care should be taken that any outliers possibly produced by the local laboratory findings are investigated at the study site.

